Study Title: Developing and Testing Implementation Strategies for Evidence-Based Obesity Prevention in Childcare
PI: [name]
Institution: University of Arkansas for Medical Sciences
Support: NIH K01 DK110141-01, Arkansas Biosciences Institute (FUNDED)
NIGMS COBRE Center for Childhood Obesity Prevention (FUNDED)

interviews at two time points: (1) between the Fall and Winter and (2) Winter and Spring fidelity assessments. We will also conduct interviews with champions and directors at enhanced sites at the conclusion of the school year. These interviews will focus on identifying remaining barriers and facilitators to WISE uptake as well as assessing feasibility and acceptability of the implementation strategy (See Director and Champion Interview Guides). Maintenance will be assessed by determining the proportion of teachers that increase or remain the same in adoption and fidelity from the initial assessment (Fall) across the school year (Winter and Spring).

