In addition to these measures collected through the K01 study, the COBRE project will support the addition of ECE Feeding Assessments at mealtimes and a baseline assessment of center climate and context. The K01 protocol only included support to assess fidelity to this core component at WISE lessons, not mealtimes. However, it is possible that ECEs' adoption (or lack thereof) of positive feeding practices at mealtimes may impact the overall effect of WISE on child outcomes. We will add two assessments of ECE Feeding Practices: Table Talk⁷⁹ and the Food Intake module of the Building Mealtime Environments and Relationships (BMER)⁸⁰ inventory. Both measures are suited for live observations to record actual ECE behavior. Table Talk quantifies ECEs' feeding communications and captures the full range of practices (i.e., not prone to ceiling effects). It captures feeding communications that are detrimental (e.g., comments that pressure children to eat more, hurry children to finish, coerce children to eat certain foods) and those that are evidence-based (e.g., direct to internal cues, support food exploration). The Food Intake module of BMER captures adult interactions that support or undermine self-regulation at meals (e.g., "Adults do not praise children for cleaning their plates."). These baseline measures will be collected in the Spring of 2018 across 4 months (Feb- May) (See Combined Mealtime Observation Forms). We will collect three assessments in each classroom to best account for potential variability due to time of year or the menu served. Prior to classroom observations, each teacher will be invited to complete a one page (front and back) survey about characteristics of her center (See Pre-WISE Context Measure). This information will be used to inform stratified randomization to treatment conditions (basic or enhanced).

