An additional secondary outcome of interest is the cost required to deliver the enhanced implementation support. Through the EBQI process, we determined the enhanced condition sites will each have a site-level champion. This champion will be a local leader in WISE implementation. Champions will receive an additional 3 hours of training to equip them to serve in this role. Champions will be supported by external facilitators from the WISE staff. The facilitators will meet with each champion in person at least once per month. Related to estimating the costs of this strategy, facilitators will track their contacts with sites (See Facilitation Log). We will also request tracking of efforts by site champions. (See Champion Log). Finally, we will ask all teachers to report monthly on their use of lesson and enhanced support materials (See Teacher Material Report). Data will be collected either through a secure RedCap Server or using paper and pencil.

Our partnering Head Start agency has 12 sites with 38 classrooms. Classrooms will be randomized to participate in either the basic (i.e., control) or enhanced implementation of WISE. Sites are all within Pulaski County and have a similar demographic make-up of ECEs and families. All families served meet the federal guideline for poverty (e.g., an annual income of \$24,250 for a family of 4). All ECEs will receive basic implementation supports (6-hour training at beginning of school year and monthly newsletter). Those randomized to the enhanced condition will receive the additional package of implementation support strategies developed in Aim 2 on a schedule agreed upon by the EBQI panel (e.g., monthly). These will be delivered by the PI or the research assistant. For both groups, we will collect child data before and after implementation. This will provide us with a matched design to assess comparative effectiveness. For both groups, the 6-hour training will be conducted in collaboration with the USDA-funded Team Nutrition project at UAMS (IRB # 206442). Their exempt training evaluation protocol will be in place. We will extract records from their database specific to our UAMS Head Start attendees, link with other study records, and then de-identify data using our coded ID system.

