Aim 3. 38 classrooms from our partnering Head Start agency will be randomized to implement the basic WISE strategy used in previous studies or the enhanced WISE strategy developed in Aim 2. Because the program is now adopting the WISE curriculum in all agency classrooms, WISE lessons are a part of normal educational activities. As such, we request a waiver of consent for these observations. In addition, 10 educators will be randomly selected and invited to provide feedback on feasibility and acceptability through semi-structured, open-ended interviews twice during the school year. We are requesting waiver of consent for these interviews as they would be the only document identifying teachers as participants in interviews. We will collect verbal consent on our audio recording. Teachers, directors, and champions will be paid \$25 for the interviews as they will take place outside of center hours.

Additionally, to assess comparative impacts on children, we will record review Body Mass Index (BMI) and Food Frequency Questionnaire (FFQ) data from the agency records at the beginning and end of the school year. We will collect a Resonance Raman Spectroscopy (RRS) assessment from children at the beginning and end of the school year as well. RRS is an optical scan of the hand to assess carotenoid intake from fruits and vegetables. It has been used safely in prior studies with children aged 3 and older. We expect to collect this information from up to 820 children between the ages of 3 and 5.

Risks and Benefits

As in all research, there exists the potential risk to study participants is the potential for loss of confidentiality. Measures to protect the confidentiality of study participants will be implemented as described in the Data Handling and Recordkeeping section below. No physical risks related to participation in this study are foreseen. Some educators may experience discomfort as a result of answering questions that they consider personal in nature. This risk will be minimized by their ability to withdraw from the study

Study Title: Developing and Testing Implementation Strategies for Evidence-Based Obesity Prevention in Childcare
PI: [name]
Institution: University of Arkansas for Medical Sciences
Support: NIH K01 DK110141-01, Arkansas Biosciences Institute (FUNDED)
NIGMS COBRE Center for Childhood Obesity Prevention (FUNDED)
or to refuse to answer any question which makes them uncomfortable.

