Aim 3. We will complete rapid coding of the semi-structured interviews with the selected ECEs at each iteration. This coding will focus on identifying aspects of the implementation feasibility and acceptability. Two coders will complete initial content analysis independently and come together to resolve any differences. These data will be combined with the fidelity data collected and presented to the EBQI panel. Changes or improvements to the enhanced strategy will be driven by these findings and the feedback from the EBQI panel.

At the completion of the study, analyses of Implementation and Effectiveness data will examine the descriptive statistics and examine outliers. Multi-level models (MLM) will be

Study Title: Developing and Testing Implementation Strategies for Evidence-Based Obesity Prevention in Childcare

PI: [name]

Institution: University of Arkansas for Medical Sciences

Support: NIH K01 DK110141-01, Arkansas Biosciences Institute (FUNDED)

NIGMS COBRE Center for Childhood Obesity Prevention (FUNDED)

used to account for the dependence among repeated observations of the same teachers in the same classroom as well as children nested within classrooms. MLM refers to a class of statistical techniques developed to analyze multi-level data structures and appropriately model clustered designs. The models will include a fixed term for intervention (basic versus enhanced) and time. Random effects will be included for the correlation of children within classrooms and the correlation of observations within teacher. This analysis will allow for estimation of variance in child outcomes accounted for by implementation (i.e., level 2) effects.

Ethical Considerations

This study will be conducted in accordance with all applicable government regulations and University of Arkansas for Medical Sciences research policies and procedures. This protocol and any amendments will be submitted and approved by the UAMS Institutional Review Board (IRB) to conduct the study.

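### Randomisation is to be stratified, but the Aim 3 model names neither the strata nor site: under classroom allocation with prognostic strata, the fidelity comparison is conservative

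*Combined protocol and SAP*

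**What the plan says.** **Design.** In Study Design and Procedures, Aim 3 (the paragraph on the COBRE additions), "each teacher will be invited to complete a one page (front and back) survey about characteristics of her center (See Pre-WISE Context Measure"). The next sentence reads: "This information will be used to inform stratified randomization to treatment conditions (basic or enhanced"). No factor, cut-point or number of strata is given. Because the survey concerns the centre, the strata are probably centre-level.

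**Analysis.** Data Analysis, Aim 3, holds the only model description: "The models will include a fixed term for intervention (basic versus enhanced) and time", and "Random effects will be included for the correlation of children within classrooms and the correlation of observations within teacher". Neither stratum nor site appears.

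**Unit of allocation.** Study Design and Procedures says "Classrooms will be randomized to participate in either the basic (i.e., control) or enhanced implementation of WISE". Study Population, Inclusion, and Exclusion agrees: "38 classrooms from our partnering Head Start agency will be randomized to implement the basic WISE strategy used in previous studies". But Study Design and Procedures also says "Through the EBQI process, we determined the enhanced condition sites will each have a site-level champion", and "We will also conduct interviews with champions and directors at enhanced sites at the conclusion of the school year". The agency has 12 sites with 38 classrooms.

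**The concern.** Stratifying on a prognostic factor removes that factor's variance from the difference between arms. A model without the factor leaves the variance in the residual, so the reported standard error exceeds the true one. Intervals come out wider than the design warrants and power is lost.

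The fidelity comparison rests on 38 classrooms, and the protocol presents the study as a preliminary step towards a later R01, so an avoidable loss of precision is worth removing.

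The site wording complicates the remedy. The right way to add the strata depends on whether classrooms or whole sites are allocated, and with one champion per enhanced site the enhanced classrooms of a site are not independent on either reading.

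**Working it through.** The plan gives no alpha, power, effect size, variance, intraclass correlation or sample-size calculation, so there is no figure of its own to reproduce.

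**Inputs from the protocol.** 12 sites, 38 classrooms, three fidelity observations per classroom, up to 820 children.

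**Assumptions.** Two-sided 5% test; about 19 classrooms per arm; classroom-mean fidelity with SD 1; a true difference of 0.8 SD for power; R2 of 0 to 0.3. For simulations with sites: ten sites of 3 classrooms and two of 4.

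**1. Classroom allocation, closed form.** With balanced repeat visits, the mixed-model arm test is in effect a t-test on classroom means. The model's SE without strata is √(2/19) = 0.324. The true SE is 0.324 × √(1 − R2). The critical value on 36 df is 2.028, so the effective cut-off is 2.028/√(1 − R2).

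| R2 | True SE | Effective cut-off | Type I error, no strata | Power, no strata | Power, two strata fitted |
|---|---|---|---|---|---|
| 0 | 0.324 | 2.028 | 5.0% | 67% | 67% |
| 0.1 | 0.308 | 2.138 | 3.9% | 68% | 72% |
| 0.2 | 0.290 | 2.267 | 3.0% | 69% | 76% |
| 0.3 | 0.271 | 2.424 | 2.1% | 70% | 82% |

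**2. Simulation of the same case**, two centre-level strata, site variance 0 to 30% of the total. Type I error without strata is 5.0–5.4%, 3.7–4.1%, 2.6–3.1% and 1.9–2.5% at R2 0, 0.1, 0.2 and 0.3. With strata it is 4.7–5.7% throughout. At R2 0.2, power rises from 67–71% to 76–79%.

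**3. Check in the plan's own model form.** REML mixed models with 38 classrooms, three visits, R2 0.3 and 300 runs give a mean SE of 0.325 without strata and 0.269 with them, against a true SD of the estimate of about 0.27. Type I error is 2.0% and 4.7%.

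**4. Classroom allocation with a shared champion.** Suppose 20–30% of enhanced-arm variance is champion-level (assumed), with site variance 10% and two strata. Strata without a site term then give type I error of 6.2–6.8% at R2 0.1 and 6.2–8.1% at R2 0.2. Without strata the figures are 4.8–5.4% and 3.6–5.1%, so the conservatism can disappear.

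**5. Whole-site allocation**, R2 0.2, two strata:

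| Site variance | Model as written | Strata, no site term | Site-level analysis with strata |
|---|---|---|---|
| 10% | 5.5% | 8.7% | 4.9% |
| 20% | 7.3% | 11.2% | 4.7% |
| 30% | 11.4% | 16.5% | 5.5% |

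These are type I errors. The excess comes from the missing site term, and adding strata alone makes it worse.

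**6. Child outcomes.** 820/38 = 21.6 children per classroom. If strata explain 20% of classroom variance, their share of the variance of a classroom mean is 0.2 × ICC/(ICC + (1 − ICC)/21.6). That is 6, 11 and 14% at assumed ICCs of 0.02, 0.05 and 0.10.

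**The case against.** **Prognostic strength is assumed.** Nothing in the documents says that the strata predict fidelity, and the protocol describes the sites as demographically alike. At R2 0 nothing is gained, and at 0.1 the gain is about 4 points of power. This stands, and it keeps the point modest. It does not remove it: the sponsor planned a survey to inform stratification, and under classroom allocation carrying the strata into the model costs almost nothing if they prove useless.

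**The model paragraph is an outline.** Listing intervention and time does not exclude other terms. That is right. A reader might infer that the sponsor decided to leave the strata out, but the text supports only under-specification.

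**The direction depends on the unit.** This is the strongest objection, and it stands. A reader might infer that the planned test is conservative whatever happens. The documents do not support that: the enhanced-site wording leaves site allocation open, and there the model as written is anti-conservative. A reader might also infer that adding the strata is enough if classrooms are allocated. The shared champion argues against that, although the champion share used above is an assumption.

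**Child outcomes gain less.** Children are measured before and after implementation. If the contrast is on change, a stratum effect that is constant over time cancels, so the gain may vanish. This also stands.

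**Conclusion.** The point holds on two conditions: classrooms are the unit of allocation, and the strata are prognostic. Then the Aim 3 model as written overstates the standard error of the fidelity comparison. Type I error is about 5, 4 or 3%, and the power lost at 0.8 SD is about 0, 4 or 8 points, at an assumed R2 of 0, 0.1 or 0.2.

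A reader might take the omission as a source of bias between arms. It is not: the loss is in precision and calibration, and it does not favour the enhanced arm.

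Importance is modest, since this is a pilot with no stated alpha or power. If whole sites are allocated, the missing site term matters more than the missing strata, and the error runs the other way. The unit must therefore be settled first.

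**What to change.** 1. Reconcile the unit of allocation between the classroom statements and the enhanced-site statements.
2. Name the stratification factors and keep them few.
3. Add to Data Analysis, Aim 3: *The Aim 3 models will include the stratification factor(s) used at randomisation as fixed effects, together with a random effect for site, with small-sample degrees of freedom.*

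Site should be random, not fixed. Under classroom allocation at R2 0.2, 11 fixed site effects gave 61% power against 76% with strata only when site variance was 0, and 73% against 77% when it was 20%. If classrooms are split within sites, the champion's effect belongs to enhanced classrooms only, so a common site effect approximates it. I have not simulated how fully it absorbs that effect.

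**Cost.** One or two sentences and no new data, plus one degree of freedom per stratum beyond the first. That is negligible with 38 allocated classrooms. With 12 allocated sites and non-prognostic strata, it is about 1 point of power for two strata (52 to 51% at site variance 10%, 45 to 44% at 20%) and 7 to 8 points for six (51 to 43%, 46 to 39%).

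The point does not call for adding the Spring 2018 mealtime observations as a covariate. Their correlation with lesson fidelity is unknown, and at a low correlation they gain nothing or cost power.

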A primary goal of this study is to improve use of evidence-based obesity prevention in childcare through development of effective implementation strategies. We will enhance knowledge of how to improve implementation, fidelity, and sustainability in these under-studied locations. Childcare shares some contextual similarities with other locations where implementation research has taken place (e.g., schools and other contexts where “paraprofessionals” provide health-related services); however, we don’t know whether lessons learned apply to childcare. Ultimately, improvements in evidence-based obesity prevention in childcare have the ability to impact 11 million children under age 5 in the US annually.³⁶ It is therefore imperative that we develop and test strategies to maximize implementation and sustainability of these practices.

Objectives

This proposal proposes the following aims:

Specific Aim 1. Identify factors associated with degree of fidelity in a previously developed and tested *basic implementation strategy* of WISE. An explanatory mixed methods approach will use secondary data to identify positive deviance and implementation failures among ECEs in a previous WISE implementation study that observed notable variability in fidelity to best practices for obesity prevention. ECEs from the prior study will be identified from quantitative fidelity observations and invited to participate in qualitative interviews to determine contextual and individual barriers and facilitators to effective implementation.

Specific Aim 2. Develop an *enhanced implementation strategy* to support uptake of the WISE intervention using stakeholder input. Based on results from Aim 1, an Evidence-Based Quality Improvement (EBQI) process¹⁸ will be used to engage stakeholders to develop implementation support strategies consistent with an implementation framework (i-PARiHS) and matched to identified barriers/ facilitators.

Specific Aim 3. Pilot test the impact of the *enhanced implementation strategy* on implementation and child health outcomes using continuous formative evaluation. We will determine whether the enhanced strategy is feasible, acceptable, and demonstrates improved implementation, fidelity, and sustainability using a Hybrid Type 3 implementation design.¹ Further, we will test the hypothesis that better WISE fidelity is positively related to child outcomes (e.g., child fruit and vegetable intake, BMI).

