Secondary outcomes will include those related to impacts of the program on children (i.e., Effectiveness). All families complete a Family Map Inventory (FMI)⁸⁶ for fall and spring assessment of family strengths and needs. For this study, the FMI will include a Food Frequency Questionnaire to assess consumption of WISE foods. BMI is a required twice-yearly, federal assessment for Head Start children. An anonymous record review of these data will provide a comparison of impacts on child diet between the basic and enhanced implementation conditions. Further, we will collect Resonance Raman Spectroscopy (RRS) scans from children with equipment leased from NuSkin. RRS is a promising alternative for measuring biomarkers where carotenoid levels are measured by an optical scan of the palm.^{87,88} Carotenoids (i.e., plant pigments) are

Study Title: Developing and Testing Implementation Strategies for Evidence-Based Obesity Prevention in Childcare

PI: [name]

Institution: University of Arkansas for Medical Sciences

Support: NIH K01 DK110141-01, Arkansas Biosciences Institute (FUNDED)

NIGMS COBRE Center for Childhood Obesity Prevention (FUNDED)

phytochemicals that provide the bright colorings to vegetables.⁸⁹ When ingested, carotenoids become biomarkers for dietary habits, evident in the makeup of cell tissues including the skin.⁹⁰ RRS measurements are reflective of dietary intake over the previous four weeks. RSS scans are sensitive to detecting individual differences of carotenoid levels^{91,92} and experimentally initiated changes.^{93,94}

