Waivers of informed consent and Health Insurance Portability and Accountability Act of 1996 (HIPAA) authorization were approved for Aims 1 and 2 of the project as this research involves no more than minimal risk to the subjects; waivers will not adversely affect the rights and welfare of the subjects; and the research could not practicably be carried out with the waiver. For these aims, the only record linking the subject and the study would be the consent document making the principal risk a breach of confidentiality.

Since the initial IRB submission, WISE has expanded from being a curriculum offered in some UAMS Head Start sites to being required by the agency in all sites and classrooms. As such, WISE is now a part of standard educational activities. Due to this shift, we are requesting a waiver of consent for teachers in Aim 3 of this project. As in Aims 1 and 2, this research involves no more than minimal risk to the subjects; and waivers will not adversely affect the rights and welfare of the subjects.

Study Title: Developing and Testing Implementation Strategies for Evidence-Based Obesity Prevention in Childcare
PI: [name]
Institution: University of Arkansas for Medical Sciences
Support: NIH K01 DK110141-01, Arkansas Biosciences Institute (FUNDED)
NIGMS COBRE Center for Childhood Obesity Prevention (FUNDED)

The Head Start teachers and staff will hand out packets to each parent at enrollment. This packet will contain the study information sheet along with the necessary paperwork the parent completes to participate in Head Start. The researchers believe that this is a good strategy for ensuring that each parent receives and reads the information sheet, as the packet is necessary information for participation in the Head Start program. The parent can return the signed form with the rest of the packet if he/she does not want his/her child to participate. We are therefore requesting a waiver of documentation of consent (e.g., "passive consent") for the child participant in Aim 3. The study is minimal risk, and involves no procedures for which written consent is normally required outside the research context.

Dissemination of Data

I will employ a multi-pronged strategy to ensure that findings from this research are disseminated to scientists and community stakeholders. These efforts will not contain any identifiable information that could be linked to a participant.

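### Child BMI and FFQ come from a record review described as anonymous, while the matched before-and-after design needs a child code that the plan does not provide

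*Combined protocol and SAP*

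**What the plan says.** All references are to the combined protocol and SAP.

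- **Source of the data.** Study Design and Procedures, Aim 3, on BMI and the FFQ in the Family Map Inventory: "An anonymous record review of these data will provide a comparison of impacts on child diet between the basic and enhanced implementation conditions". Study Population, Aim 3, repeats the record review, timed to the start and close of the school year, without the word anonymous: "we will record review Body Mass Index (BMI) and Food Frequency Questionnaire (FFQ) data from the agency records at the beginning and end".
- **Design claimed.** Study Design and Procedures, Aim 3, on child data taken before and after implementation in both groups: "This will provide us with a matched design to assess comparative effectiveness".
- **Model.** Data Analysis, Aim 3: "The models will include a fixed term for intervention (basic versus enhanced) and time". It continues: "Random effects will be included for the correlation of children within classrooms and the correlation of observations within teacher". No term is named for the two measurements of one child.
- **Fidelity hypothesis.** Objectives, Specific Aim 3: "we will test the hypothesis that better WISE fidelity is positively related to child outcomes", with fruit and vegetable intake and BMI as examples.
- **Coding.** Study Design and Procedures, Aim 3, describes a coded route for the teachers' training records: "link with other study records, and then de-identify data using our coded ID system". Data Handling and Recordkeeping says that responses carry no identifying link, and also that listed staff hold a code identifying the subject. Neither statement is tied to the child agency records.
- **Opt-out.** Ethical Considerations: "The parent can return the signed form with the rest of the packet if he/she does not want his/her child to participate".

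The plan does not say which codes the BMI and FFQ extract carries, how Fall and Spring records are joined, or who removes opted-out children from it.

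**The concern.** A matched analysis needs a key that follows each child from Fall to Spring. The plan describes such a key for teacher training records but uses the word anonymous for the child records. A data manager or IRB could fairly read that as ruling out a linkable child code. If the Fall extract is released on that reading, the study team may be unable to pair the records later without returning to the agency.

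The gap matters in four ways:

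- Each child's Fall value is collected but cannot be used to adjust that child's Spring value.
- BMI and FFQ cannot be set beside the same child's RRS scan.
- Children who join or leave during the year cannot be told apart from those present throughout, so a change in roster can look like a change in outcome.
- A model with no child term treats a child's two records as if they came from different children in the same class.

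**Working it through.** The documents state no sample size calculation, power, ICC or within-child correlation, so there is no planned figure to reproduce. The first step is to ask what each promised analysis needs.

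| Promised analysis | Key needed on the BMI/FFQ record |
|---|---|
| Basic versus enhanced | Arm label, which derives from the randomized classroom |
| Children nested in classrooms | Classroom label |
| Fidelity against child outcome | Classroom or teacher label |
| Matched before-and-after comparison | Child code common to Fall and Spring |
| Comparison with the child's RRS scan | Child code common to all three measures |

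A literally anonymous extract fails the last two rows. The first three need no child code.

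**Size of the loss when classroom labels are kept and the child code is not**

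Inputs from the documents: up to 820 children and 38 classrooms, so m = 820/38 = 21.6 children per classroom.

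Assumed inputs:
- k = 19 classrooms per arm (38/2)
- two-sided 5% test and 80% power
- ICC 0.01 to 0.10
- classroom autocorrelation rc = 0.8
- within-child correlation rs = 0.5 to 0.9
- the target is the arm-by-time contrast, which the before-and-after comparison implies although the model sentence names no interaction

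In SD units:

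SE = √{2 × (2/k) × [ICC(1 − rc) + (1 − ICC)(1 − rs)/m]}

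With no child term in the model, rs is set to 0.

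Example with ICC 0.05 and rs 0.7:
- Linked: √{0.2105 × [0.05 × 0.2 + 0.95 × 0.3/21.6]} = √(0.2105 × 0.0232) = 0.070
- Unlinked: √{0.2105 × [0.05 × 0.2 + 0.95/21.6]} = √(0.2105 × 0.0540) = 0.107
- Ratio: 1.53

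The minimum detectable difference (MDD) in change is (1.96 + 0.84) × SE.

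| ICC | rs | SE linked | SE unlinked | Ratio | MDD linked → unlinked (SD) |
|---|---|---|---|---|---|
| 0.01 | 0.5 | 0.072 | 0.100 | 1.39 | 0.20 → 0.28 |
| 0.01 | 0.7 | 0.058 | 0.100 | 1.74 | 0.16 → 0.28 |
| 0.01 | 0.9 | 0.037 | 0.100 | 2.70 | 0.10 → 0.28 |
| 0.05 | 0.5 | 0.082 | 0.107 | 1.30 | 0.23 → 0.30 |
| 0.05 | 0.7 | 0.070 | 0.107 | 1.53 | 0.20 → 0.30 |
| 0.05 | 0.9 | 0.055 | 0.107 | 1.94 | 0.15 → 0.30 |
| 0.10 | 0.5 | 0.093 | 0.114 | 1.23 | 0.26 → 0.32 |
| 0.10 | 0.7 | 0.083 | 0.114 | 1.38 | 0.23 → 0.32 |
| 0.10 | 0.9 | 0.071 | 0.114 | 1.60 | 0.20 → 0.32 |

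The unlinked figure is the SE that the model would report. If exactly the same children are measured twice, the change in a class mean equals the mean of the children's changes. An analysis of class-mean change then recovers the linked SE with no child code. The ratios are therefore the cost of fitting the model without a child term. They are not an unavoidable loss of information.

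**The case against.** The best defense is that the word anonymous is used loosely. Study Population, Aim 2, applies it to audio-recorded panel sessions with recruited, paid members, where it can hardly mean unlinkable. Study Population, Aim 3, describes the child record review without it, and Data Handling and Recordkeeping mentions a subject code. Records without names can still carry an arbitrary code. All of this stands, and it makes the problem a contradiction in the text rather than a proven impossibility. It does not supply the missing key, because no statement about a code is tied to the child records.

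It is also true that the model as written needs only classroom or teacher labels, and that class-mean change on a stable roster avoids most of the precision loss. The need for a child code comes from the matched-design claim, and the missing child term is a gap of its own.

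A reader might go further and infer three things that the documents do not support:

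- **That the fidelity hypothesis cannot be tested on BMI or FFQ.** Fidelity is observed on teachers, so a classroom label is enough. Nothing says that label is stripped, and a comparison of arms already implies a label derived from the classroom.
- **That the opt-out cannot be applied.** The forms return to Head Start with the enrollment packet, and the records are the agency's. The agency could drop those children before release. The plan is silent on this step, not incapable of it.
- **That the type I error rises to 17%.** With ICC 0.05 the design effect is 1 + 20.6 × 0.05 = 2.03, and 2[1 − Φ(1.96/√2.03)] = 17%. The arithmetic is right, but it describes an analysis that ignores classrooms. Data Analysis, Aim 3, specifies a random effect for children within classrooms.

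**Conclusion.** The concern holds as an unresolved conflict between anonymous child records and a matched design, together with a model that has no child-level term. With classroom labels kept, valid inference on arms and on fidelity remains possible. What is at risk is precision, child-level baseline adjustment, the link to RRS and the handling of joiners and leavers.

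Under the assumptions listed, the model SE of the arm-by-time contrast is about 1.2 to 2.7 times that of a linked analysis. The detectable difference moves from 0.10–0.26 SD to 0.28–0.32 SD. Class-mean analysis with stable rosters would recover much of this. The correlations are assumed, and the documents give no roster turnover.

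The weight is moderate. BMI and FFQ are secondary outcomes of a pilot, and the study team collects the RRS scans itself. The point is still worth correcting before extraction, because the remedy is cheap and uses data already planned.

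**What to change.** 1. In Study Design and Procedures, Aim 3, describe the BMI and FFQ data as coded instead of anonymous.
2. State that the agency releases Fall and Spring records under one study ID per child plus a classroom ID, and that the RRS scan carries the same child ID. Say who holds the key, and reconcile the two statements on codes in Data Handling and Recordkeeping.
3. State in Ethical Considerations that the agency removes opted-out children before release.
4. In Data Analysis, Aim 3, keep the classroom clustering and either analyse Spring values adjusted for the child's Fall value or add a child random effect. Choose one in advance and say how children with only one of the two measurements are treated.

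The cost is a change of wording and an IRB amendment from anonymous to coded data. A coded-ID system is already described for the teacher training records, and no additional measurement is needed.
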